The MMRM model will include treatment, strata (country, CGM use prior to study entry [yes/no], and carbohydrate counting for prandial insulin dosing [yes/no]), visit and treatment-by-visit interaction as fixed effects, and baseline of the dependent variable (HbA1c) as a covariate.

The Kenward-Roger approximation will be used to estimate denominator degrees of freedom for the MMRM models. An unstructured covariance structure will be used to model the within-participant errors. If this structure fails to converge, the following covariance structures will be used in order until one converges:

1. Toeplitz with heterogeneity
2. autoregressive with heterogeneity
3. compound symmetry with heterogeneous variances
4. Toeplitz
5. autoregressive, and
6. compound symmetry without heterogeneous variances.

The 2-sided 95% CI of the LS mean for individual treatment groups and treatment LS mean difference for the HbA1c change from baseline to Week 26 (Visit 22) will be estimated. For both estimands, LY3209590 will be declared noninferior to insulin degludec if the upper limit of the 2-sided 95% CI for the LS mean difference in the HbA1c change from baseline is below NIM (+0.4% or +0.3% for different regulatory requirements).

The HbA1c is reported in % units and will be converted to mmol/mol using this formula.

$$\text{HbA1c in mmol/mol} = 10.93 \times \text{HbA1c in \%} - 23.5 \text{ (NGSP IFCC Standardization of HbA1c page [www.ngsp.org/ifccngsp.asp])}$$

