1.2. Study Design

- Study BDCY is a Phase 3, open-label, 2-arm, parallel-design, randomized control study to investigate if LY3209590 is noninferior to insulin degludec in adult participants with T1D who are treated with basal-bolus insulin MDI therapy.
- This study consists of a 1-week screening period, a 2-week lead-in period, a 52-week treatment period, and a 5-week safety follow-up period.
- Participants will be randomly assigned in a 1:1 ratio to LY3209590:insulin degludec. All participants will be treated with basal-bolus MDI therapy, which will be titrated to glycemic targets and as clinically indicated for hyperglycemia.
- Participants will be stratified based on country, HbA1c stratum (<8% and \geq 8%) at screening Visit 1, CGM use prior to study entry (yes/no), and carbohydrate counting for prandial insulin dosing (yes/no).
- Rescue therapy will be considered during the treatment period if the participants meet the protocol criteria of severe, persistent hyperglycemia.
- If study intervention is permanently discontinued, the participant will be encouraged to continue participation in the study for continued monitoring. Both efficacy (including HbA1c) and safety data will continue to be collected per the schedule of activities in the protocol.

2. Statistical Hypotheses

The primary objective of this study is to test the hypothesis that LY3209590 is noninferior to insulin degludec on glycemic control as measured by change in HbA1c from baseline to Week 26 (Visit 22) in adults with T1D currently on basal-bolus insulin MDI therapy.

The null hypothesis ($H_{1,0}$) is the difference between LY3209590 and insulin degludec in the change in HbA1c from baseline to Week 26 (Visit 22) is greater than the noninferiority margin (NIM).

The NIMs of 0.4% and 0.3% will both be tested to meet different regulatory requirements. A 2-sided 95% confidence interval (CI) will be used for testing noninferiority.

Secondary hypotheses

The key secondary (multiplicity adjusted) objectives are to test the hypotheses that LY3209590 is superior to insulin degludec with respect to

- change in HbA1c from baseline to Week 26 (Visit 22)
 - $H_{2,0}$: the difference (LY3209590 - insulin degludec) ≥ 0.0
- time in glucose range between 70 and 180 mg/dL (3.9 and 10.0 mmol/L), inclusive, measured by CGM 4 weeks prior to Week 26 (Visit 22)
 - $H_{3,0}$: the difference (LY3209590 - insulin degludec) ≤ 0.0 , and

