2.1. Multiplicity Adjustment

A graphical approach (Bretz et al. 2009, 2011) for multiple comparisons will be used to ensure the strong control of the overall type 1 error rate for testing the primary and key secondary (multiplicity adjusted) objectives. The overall significance level (α) will be set to 0.05. The total α will be used for the primary objective first, then the α will be allocated and transitioned to other key secondary objectives once the primary objective is met. Therefore, the noninferiority test for the primary objective will be based on the 2-sided 95% CI. Once the upper limit of the 2-sided 95% CI is below the NIM, the noninferiority will be achieved, and the α of 0.05 will be distributed to test superiority for the key secondary objectives. If the p-value of the 2-sided test for one of the key secondary objectives is below the assigned α level, the superiority is demonstrated, and the assigned α level will be distributed to the remaining objectives. The iterative test procedure continues until none of the remaining objectives can be demonstrated with their preserved α or all objectives are demonstrated successful. The NIM of 0.4% (for the treatment regimen estimand) and 0.3% (for the efficacy estimand) will both be tested to meet different regulatory requirements. No multiplicity adjustments will be made for conducting separate analyses relative to the efficacy and treatment regimen estimands. Each estimand will have its own familywise error rate of 0.05.

For primary and key secondary efficacy objectives, the details of the type 1 error control strategy are illustrated in [Figure BDCY.2.1](#). No multiplicity adjustments will be made for evaluating other secondary and exploratory objectives, or for safety assessments.

[figure not shown]

Figure BDCY.2.1. Type 1 error control strategy for primary and key secondary efficacy endpoints.

3. Analysis Sets

The following analysis populations and datasets are defined for the purpose of analysis.

Analysis Populations/ Datasets	Description
Entered Population	All participants who sign the informed consent form.
Randomized Population	All randomized participants. Participants will be analyzed according to the treatment they were assigned.
Modified Intent-to-Treat (mITT) Population	All randomized participants who took at least 1 dose of LY3209590 or insulin degludec. Participants will be analyzed according to the treatment they were assigned.

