Analysis Model	After the imputation, the observed and imputed data will be analyzed by the ANCOVA model using treatment, strata (country, CGM use prior to study entry [yes/no], and carbohydrate counting for prandial insulin dosing [yes/no]), and baseline value of the dependent variable as independent variables. The statistical inference will be based on the multiple imputation framework by Rubin ^b .	The MMRM model will include treatment, strata (country, baseline, CGM use prior to study entry [yes/no], and carbohydrate counting for prandial insulin dosing [yes/no]), and visit and treatment-by-visit interaction as fixed effects and baseline of the dependent variable as a covariate. The Kenward-Roger approximation will be used to estimate denominator degrees of freedom for the MMRM models. An unstructured covariance structure will be used to model the within-participant errors. If this structure fails to converge, the following covariance structures will be used in order until one converges: 
 1. Toeplitz with heterogeneity 2. autoregressive with heterogeneity 3. compound symmetry with heterogeneous variances 4. Toeplitz 5. Autoregressive, and 6. compound symmetry without heterogeneous variances.

Abbreviations: ANCOVA = analysis of covariance; CGM = continuous glucose monitoring; EAS1 = Efficacy Analysis Set 1; HbA1c = hemoglobin A1c; EAS2 = Efficacy Analysis Set 2; MMRM = mixed model of repeated measures.

^a (Qu and Dai 2022)

^b (Rubin 1987)

The 2-sided 95% CI of the LS mean difference (LY3209590 - insulin degludec) in the HbA1c change from baseline to Week 26 (Visit 22) will be estimated. For both estimands, LY3209590 will be declared noninferior to insulin degludec if the upper limit of the 2-side 95% CI for the LS mean difference in the HbA1c (measured in %) change from baseline is below the NIM of +0.4%. In addition, the 95% CI for the LS mean difference will be compared to an alternative NIM of +0.3%.

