4.9. Changes to Protocol-Planned Analyses

There are no changes but additional details are provided to the analyses described in the protocol.

5. Sample Size Determination

Approximately 670 participants will be randomized to LY3209590 and insulin degludec in a 1:1 ratio. With the assumption of 15% dropout at Week 26, approximately 284 and 284 participants will complete 26 weeks of treatment on LY3209590 and insulin degludec, respectively.

The primary objective of this study is to test the hypothesis that LY3209590 is noninferior to insulin degludec on glycemic control as measured by change from baseline to Visit 22 (Week 26) in HbA1c in participants with T1D currently basal-bolus insulin.

Assuming an NIM of 0.4%, no true difference between treatment groups, and an SD of 1.1%, 568 completers (284 on LY3209590 and 284 on insulin degludec) will provide at least 99% statistical power to show noninferiority between LY3209590 and insulin degludec using the upper limit of a 2-sided 95% CI (LY3209590 - insulin degludec). This sample size also has at least 90% statistical power to show noninferiority between LY3209590 and insulin degludec using a 0.3% NIM at Week 26.

The 568 completers will provide 90% statistical power to demonstrate the superiority (LY3209590 vs insulin degludec) of change in HbA1c from baseline to 26 weeks (assuming an SD of 1.1% and true mean difference of -0.3%) using the α of 0.05.

The 568 completers will provide at least 99% statistical power to show the superiority of the percentage of time in glucose range between 70 and 180 mg/dL (3.9 and 10.0 mmol/L), inclusive, measured by CGM 4 weeks prior to Week 26 between LY3209590 and insulin degludec (assuming an SD of 10% and true mean difference of 5%) using the α of 0.05.

The 568 completers will provide 80% statistical power to show the superiority of the event rate of clinically significant nocturnal hypoglycemia (<54 mg/dL [3.0 mmol/L] or severe) during the treatment phase up to Week 52 (assuming event rates of 3.37 [SD = 7.13] and 4.87 [SD = 7.13] events per participant per year for LY3209590 and insulin degludec, respectively) using a negative binomial distribution α of 0.05.

6. Supporting Documentation

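### For the efficacy estimand, SAP 2.1 sets the noninferiority margin at 0.3% but SAP 4.3.2 declares noninferiority at 0.4%, so an upper limit from 0.3% to below 0.4% gives opposite primary verdicts

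*SAP*

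**What the plan says.** SAP 2.1 (Multiplicity Adjustment) ties each margin to an estimand: "The NIM of 0.4% (for the treatment regimen estimand) and 0.3% (for the efficacy estimand) will both be tested". The same paragraph sets the gate to the key secondary tests: "Once the upper limit of the 2-sided 95% CI is below the NIM, the noninferiority will be achieved", after which the alpha of 0.05 is distributed. Each estimand has its own familywise error rate of 0.05.

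SAP 4.3.2 (Main Analytical Approach) gives a different rule: "For both estimands, LY3209590 will be declared noninferior to insulin degludec if the upper limit of the 2-side 95% CI" for the LS mean difference, "measured in %) change from baseline is below the NIM of +0.4" (percent). It then adds: "In addition, the 95% CI for the LS mean difference will be compared to an alternative NIM of +0.3" (percent).

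Other places name both margins without assigning either to an estimand. SAP 2 (Statistical Hypotheses) says "The NIMs of 0.4% and 0.3% will both be tested to meet different regulatory requirements". Protocol 9.3.2 requires the upper limit to be "below NIM (+0.4% or +0.3% for different regulatory requirements".

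SAP 4.3.2 also allots the treatment-regimen estimand to the FDA submission and the efficacy estimand to registrations elsewhere.

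**The concern.** The two SAP sections cannot both govern the efficacy estimand. By 2.1 its margin is 0.3%. By 4.3.2 the declaration is made at 0.4%, and 0.3% is only a further comparison. An efficacy-estimand upper limit of, say, 0.35% would be declared noninferior under 4.3.2 and not under 2.1.

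This is the success criterion for the primary objective outside the US. It is also the gate in the multiplicity graph, where 2.1 speaks of a single margin whose crossing releases alpha. If the conflict is settled only after the result is known, the primary threshold becomes a post hoc choice, in an open-label trial.

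**Working it through.** **Which places conflict**

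| Source | Treatment-regimen estimand | Efficacy estimand |
|---|---|---|
| SAP 2.1 | 0.4% | 0.3% |
| SAP 4.3.2, declaration | 0.4% | 0.4% |
| SAP 4.3.2, additional comparison | 0.3%, called alternative | 0.3%, called alternative |
| SAP 4.3.3.1, imputation under the null | 0.4 | not covered |
| SAP 2; Protocol 9.1 and 9.3.2 | both margins, not assigned | both margins, not assigned |

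The treatment-regimen estimand is consistently declared at 0.4%. The conflict concerns the efficacy estimand only. Both rules require the limit to be below the margin, so the zone of disagreement is 0.3 ≤ upper limit < 0.4. SAP 4.9 reports no changes to the protocol analyses and sets no order of precedence.

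**Inputs (SAP 5, same in Protocol 9.5):** 284 completers per arm, SD 1.1%, true difference 0, upper limit of a two-sided 95% CI.

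**Step 1. Standard error.** SE = 1.1 × √(2/284) = 0.0923. CI half-width = 1.96 × 0.0923 = 0.181.

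**Step 2. Reproduce the stated powers.** Power = Φ(margin/SE − 1.96).
- Margin 0.4: Φ(2.373) = 0.9912 (noncentral t, 566 df: 99.1%). Stated: at least 99%.
- Margin 0.3: Φ(1.290) = 0.9015 (noncentral t: 90.1%). Stated: "This sample size also has at least 90% statistical power to show noninferiority between LY3209590 and insulin degludec using a 0.3% NIM".

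Both reproduce, so the sample size is not in question.

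**Step 3. Zone of disagreement for the point estimate.** 0.3 − 0.181 = 0.119 to 0.4 − 0.181 = 0.219. Every estimate in the zone is above 0, so HbA1c superiority fails under either rule. The key secondary tests at stake are time in range and nocturnal hypoglycemia.

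**Step 4. Probability of opposite verdicts.** For true difference d, P = Φ((0.4 − d)/SE − 1.96) − Φ((0.3 − d)/SE − 1.96). At d = 0: 0.9912 − 0.9015 = 0.0897, or 9.0%.

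**Step 5. Sensitivity.** Apart from d = 0, d = −0.3 and SD 1.1, these values are assumptions that the documents do not give.

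| True difference (SD 1.1) | −0.3 | −0.10 | −0.05 | 0 | 0.05 | 0.10 | 0.15 |
|---|---|---|---|---|---|---|---|
| P(disagree) | 0.0003% | 0.9% | 3.2% | 9.0% | 19.4% | 32.0% | 40.4% |

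The −0.3 is the plan's own assumption for HbA1c superiority.

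| SD (true difference 0) | 0.8 | 0.9 | 1.0 | 1.1 | 1.2 |
|---|---|---|---|---|---|
| P(disagree) | 0.6% | 2.2% | 5.1% | 9.0% | 13.2% |

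**Step 6. Error rates.** Each rule has 2.5% one-sided error against its own margin. Only if 0.3% is the required margin does the 4.3.2 rule look liberal: at a true difference of 0.3 it declares noninferiority with probability Φ(0.1/0.0923 − 1.96) = 19.0%, against 2.5% under 2.1.

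**The case against.** The strongest reply is that little changes in practice. There is one model and one CI, both thresholds are fixed in advance, and 4.3.2 already commits to the 0.3% comparison. An upper limit of 0.35% would be shown as meeting 0.4% and missing 0.3% whichever section is followed. That stands as far as reporting goes. It does not say which comparison is the primary declaration, and 4.3.2 gives that role to 0.4% for both estimands.

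A second reply is that the alpha gate is described only in 2.1, where the margin most naturally reads as 0.3% for the efficacy estimand. The version history also says that 2.1 was expanded in version 2 to finalize the multiplicity strategy. This makes 0.3% the likelier reading of the gate, but it is not a rule of precedence, and a declaration made under 4.3.2 would dispute it. Figure BDCY.2.1 was not available for this review and might label the gate's margin. Even so, the two texts would still conflict.

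A third reply concerns size. The 9.0% falls quickly if the true difference favours LY3209590 or if the SE is smaller, as the tables show. It is also only an upper bound, at a true difference of 0, on the chance that a key secondary conclusion changes. All of that is right. It limits how often the conflict would bite but does not remove it.

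Finally, no inflation of type I error is shown. None is claimed: the 19.0% figure holds only if 0.3% is the required margin.

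**Conclusion.** The concern holds. For the efficacy estimand the SAP states its primary decision threshold in two incompatible ways, and nothing else in the text of either document resolves them. At the plan's own noninferiority inputs the two sections give opposite verdicts with probability 9.0%, for point estimates of about +0.119 to +0.219. This rests on SD 1.1%, a true difference of 0 and the unadjusted completer SE. The planned MMRM adjusts for baseline and strata, so the actual SE, and with it this probability, may be smaller. The treatment-regimen estimand, the sample size and the stated powers are sound on this point. The matter must be fixed because it determines the primary verdict outside the US and whether alpha reaches time in range and nocturnal hypoglycemia.

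**What to change.** Before unblinding, state one declaring margin for each estimand, in identical words in SAP 2.1 and SAP 4.3.2, and say which comparison releases alpha in the graph. The simplest alignment is to 2.1, the only section that maps margins to estimands: 0.4% for treatment regimen, 0.3% for efficacy. The documents do not prove which was intended; if the sponsor means 0.4% for both, 2.1 should be corrected instead. Keep reporting the CI against the other margin for regulators that need it, and state that this second comparison does not release alpha. Check that Figure BDCY.2.1 agrees.

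The cost is about two sentences of SAP text. The sample size is unchanged, and power for the efficacy estimand is one of the two figures already stated: at least 90% if 0.3% governs, at least 99% if 0.4% governs.

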4.3.3. Sensitivity Analysis

4.3.3.1. Two-way Tipping Point Analysis

To confirm the robustness of the primary endpoint results in treatment regimen estimand, a 2-way tipping point analysis represents varying assumptions for missing data from both treatment groups will be conducted. This sensitivity analysis will focus on missing data at the primary endpoint. Penalties for imputed missing values will be added for both treatment arms. The ANCOVA model for treatment regimen estimand will be conducted after the penalties are added. The multiple imputation framework by Rubin (1987) will be used to summarize the results. The corresponding p-value of the noninferiority test will be shown by color scale in the figure.

Additionally, after imputing the missing data used in the treatment-regimen estimand (Section 4.3.2), imputation under the noninferiority null hypothesis will be conducted by adding 0.4 (NIM) to the same imputed data for the LY3209590 group only. The ANCOVA model for the treatment-regimen estimand will be rerun using the adjusted data. The multiple imputation framework by Rubin (1987) will be used to summarize the results.

4.3.3.2. Including Inadvertently Enrolled Participants

The primary efficacy analysis will be repeated for the mITT population, including inadvertently enrolled participants, for both treatment regimen estimand and efficacy estimand.

4.3.4. Supplementary Analyses

Additional analysis may be conducted as needed.

4.4. Secondary Endpoint Analysis

4.4.1. Key Secondary Endpoints

A graphical approach (Bertz et al. 2009, 2011) will be used to control the overall type 1 error for the primary objective and test the superiority of LY3209590 compared with insulin degludec for

- 1) change from baseline in HbA1c at Week 26 (Visit 22)
- 2) time in glucose range between 70 and 180 mg/dL, inclusive, measured by CGM 4 weeks prior to Week 26 (Visit 22), and
- 3) the event rate of clinically significant nocturnal hypoglycemia (<54 mg/dL or severe) during the treatment phase up to Week 52 (Visit 29).

4.4.1.1. Definition of Endpoint(s)

See Section 4.3.1 for HbA1c change from baseline to Week 26 (Visit 22).

The time in glucose range between 70 and 180 mg/dL, inclusive, will be based on the percentage of CGM readings within the glucose range in the 4 weeks prior to Week 26. The derivation of CGM parameters is provided in Appendix 6 (Section 6.6).

The hypoglycemia events will be based on participant entry into an electronic diary, which receives all blood glucose (BG) measurements performed by the participant and transmits via Bluetooth from the study-provided glucometer. The nocturnal period is defined by midnight to 0600. The event rate of nocturnal hypoglycemia will be based on the count of the hypoglycemia episodes in the clinically significant nocturnal period and the corresponding exposure of study intervention.

4.4.1.2. Main Analytical Approach

The superiority test in change from baseline to Week 26 (Visit 22) in HbA1c will be based on the same primary endpoint analysis described in Section 4.3.2.

The time in glucose range between 70 and 180 mg/dL, inclusive, measured by CGM will be analyzed using an ANCOVA model for the treatment-regimen estimand (using data from EAS1) and an MMRM model for the efficacy estimand (using data from EAS2). The analyses are

similar to the primary analysis described in Section 4.3.2 with additional term of baseline HbA1c stratum ($<8.0\%$, $\geq8.0\%$) in analysis models. For the treatment-regimen estimand, only participants with an observation at baseline or at Week 26 (Visit 22) will be included in the analysis. The missing data at baseline will be imputed using multiple imputation with assumption of missing at random. Missing data at Week 26 (Visit 22) will be imputed by multiple imputation with the approach similar to the imputation used for the primary endpoint.

The rate of participant-reported nocturnal hypoglycemia will be analyzed by a negative binomial regression. The analysis details are provided in Section 4.6.3.1.1.

4.4.1.3. Sensitivity Analysis

The analyses described in Section 4.4.1.2 will be repeated for both the treatment regimen estimand and efficacy estimand by including inadvertently enrolled participants using mITT population.

4.4.2. Supportive Secondary Endpoints

4.4.2.1. Other Efficacy Endpoints

The analysis of change from baseline for HbA1c at Week 52, fasting glucose by self-monitored blood glucose (SMBG) at Weeks 26 and 52, CGM (except for variability) parameters at Weeks 26 and 52 will be performed for both treatment regimen estimand and efficacy estimand.

For treatment regimen estimand, only participants with an observation at baseline or at the endpoint visit will be included in the analysis. The missing baseline will be imputed using multiple imputation under assumption of missing at random. Missing data at the endpoint visit will be imputed using either retrieved dropout or return-to-baseline multiple imputation approach determined by the criterion described for the primary efficacy endpoint in Section 4.3.2. ANCOVA analysis will be conducted similar to that for the primary endpoint. An additional term of baseline HbA1c stratum ($<8.0\%$, $\geq8.0\%$) will be added into the model for the endpoints other than HbA1c.

For efficacy estimand, participants with baseline and at least 1 post baseline observation will be included in the analysis. The longitudinal observations of actual and change from baseline in HbA1c up to Week 52 will be analyzed using the same MMRM model as for the efficacy estimand described in Section 4.3.2. The analyses of other continuous efficacy measures (insulin dose, fasting glucose, and CGM parameters) will use an MMRM model similar to that for the primary endpoint with an additional term of baseline HbA1c stratum ($<8.0\%$, $\geq8.0\%$). The variance-covariance structure in the MMRM models for fasting glucose from SMBG and insulin dose will be based on compound symmetry.

Additional analyses are as specified below.

